4.5 Subject Withdrawal/Discontinuation Criteria

In this study, MK-3475 administration will continue until one of the following conditions is observed.

4.5.1. Disease progression [iRECIST Criteria]

Disease progression is defined as rapid growth of multiple measurable, non-measurable or new lesions, or at least a 20% increase in the sum of diameters of target (measurable) lesions, taking as

reference the smallest sum on study (this includes the baseline sum if that is the smallest on study). In addition to the relative increase of 20%, the sum must also demonstrate an absolute increase of at least 5 mm. (Note: the appearance of one or more new lesions is also considered progression).

4.5.2 Noncompliance:

If the patient is not able to compliant with the treatment schedule in the absence of toxicity, the study treatment should be discontinued for the patient.

4.5.3. Sustained side effects:

Study treatment will be discontinued for patients who have sustained toxic effects that are attributed to the study drug and require a dose interruption lasting more than 12 weeks.

4.5.4. Initiation of new anticancer treatment:

In patients for whom the investigator, in his or her judgment, determines new treatment for breast cancer is warranted, the study treatment may be discontinued.

4.5.5. Patient withdraws consent.

In the event that a patient withdraws consent, the reason(s) for withdrawal must be documented. Patients must be informed that their participation in the study is voluntary and that they may choose not to take part in the study or to stop taking part at any time. If a patient chooses not to take part in the study or to stop at any time, his/her future medical care or medical benefits will not be affected.

4.5.6. Patient has completed 24 months of treatment.

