Complete response, partial response, or stable disease	Cannot have met criteria for progression before complete response, partial response, or stable disease	Can have had iUPD (one or more instances), but not iCPD, before iCR, iPR, or iSD
Confirmation of complete response or partial response	Only required for non-randomised trials	As per RECIST 1.1
Confirmation of stable disease	Not required	As per RECIST 1.1
New lesions	Result in progression; recorded but not measured	Results in iUPD but iCPD is only assigned on the basis of this category if at next assessment additional new lesions appear or an increase in size of new lesions is seen (≥ 5 mm for sum of new lesion target or any increase in new lesion non-target); the appearance of new lesions when none have previously been recorded, can also confirm iCPD
Independent blinded review and central collection of scans	Recommended in some circumstances—eg, in some trials with progression-based endpoints planned for marketing approval	Collection of scans (but not independent review) recommended for all trials
Confirmation of progression	Not required (unless equivocal)	Required
Consideration of clinical status	Not included in assessment	Clinical stability is considered when deciding whether treatment is continued after iUPD

Table 5: Assignment of timepoint response using iRECIST

	Timepoint response with no previous iUPD in any category	Timepoint response with previous iUPD in any category*
Target lesions: iCR; non-target lesions: iCR; new lesions: no	iCR	iCR
Target lesions: iCR; non-target lesions: non-iCR/non-iUPD; new lesions: no	iPR	iPR
Target lesions: iPR; non-target lesions: non-iCR/non-iUPD; new lesions: no	iPR	iPR
Target lesions: iSD; non-target lesions: non-iCR/non-iUPD; new lesions: no	iSD	iSD
Target lesions: iUPD with no change, or with a decrease from last timepoint; non-target lesions: iUPD with no change, or decrease from last timepoint; new lesions: yes	Not applicable	New lesions confirm iCPD if new lesions were previously identified and they have increased in size (≥ 5 mm in sum of measures for new lesion target or any increase for new lesion non-target) or number; if no change is seen in new lesions (size or number) from last timepoint, assignment remains iUPD

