Target lesions: iSD, iPR, iCR; non-target lesions: iUPD; new lesions: no	iUPD	Remains iUPD unless iCPD is confirmed on the basis of a further increase in the size of non-target disease (does not need to meet RECIST 1.1 criteria for unequivocal progression)
Target lesions: iUPD; non-target lesions: non-iCR/non-iUPD, or iCR; new lesions: no	iUPD	Remains iUPD unless iCPD is confirmed on the basis of a further increase in sum of measures ≥ 5 mm; otherwise, assignment remains iUPD
Target lesions: iUPD; non-target lesions: iUPD; new lesions: no	iUPD	Remains iUPD unless iCPD is confirmed based on a further increase in previously identified target lesion iUPD in sum of measures ≥ 5 mm or non-target lesion iUPD (previous assessment need not have shown unequivocal progression)

Target lesions: iUPD; non-target lesions: iUPD; new lesions: yes	iUPD	Remains iUPD unless iCPD is confirmed on the basis of a further increase in previously identified target lesion iUPD sum of measures ≥ 5 mm, previously identified non-target lesion iUPD (does not need to be unequivocal), or an increase in the size or number of new lesions previously identified
Target lesions: non-iUPD or progression; non-target lesions: non-iUPD or progression; new lesions: yes	iUPD	Remains iUPD unless iCPD is confirmed on the basis of an increase in the size or number of new lesions previously identified

* non-iCR/non-iUPD = criteria for neither CR nor PD have been met.

4.6.2. Response will not be considered evaluable in the following categories:

4.6.2.1. Early Deaths: Patients who die within the first 2 weeks of the initiation of drug therapy owing to concurrent disease. These cases will be considered treatment failures in the intent-to-treat analysis.

4.6.2.2. Lost to Follow-up: Patients for whom there is inadequate information to judge tumor response because of loss of contact with our institution (>2 months after a missed appointment) and with referring physician in spite of repeated attempts to locate them. These cases will be considered treatment failures in the intent-to-treat analysis.

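### Section 4.5.1 is headed iRECIST but stops MK-3475 at an unconfirmed finding that Tables 4 and 5 classify as iUPD, with no place for clinical stability

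*Combined protocol and SAP*

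**What the plan says.** Section 4.5 states the dosing rule: "MK-3475 administration will continue until one of the following conditions is observed". The first condition is Section 4.5.1, whose heading names the iRECIST criteria. It has three limbs: rapid growth of multiple lesions; a rise of at least 20% and at least 5 mm in the target-lesion sum from its smallest value on study; and a note that "the appearance of one or more new lesions is also considered progression". It does not mention iUPD, iCPD, a confirming scan or clinical stability.

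Section 4.6.1 adopts iRECIST for treatment response. In Table 4, the new-lesions row reads "Result in progression; recorded but not measured" under RECIST 1.1. Under iRECIST the same row reads "Results in iUPD but iCPD is only assigned on the basis of this category if at next assessment additional new lesions appear" (or the recorded new lesions grow). Other rows of Table 4 make confirmation of progression a requirement under iRECIST, and state that "Clinical stability is considered when deciding whether treatment is continued after iUPD". On later response, the iRECIST column says that a patient "Can have had iUPD (one or more instances), but not iCPD, before iCR, iPR, or iSD". Table 5 gives the rule for a target-lesion increase already coded iUPD: "Remains iUPD unless iCPD is confirmed on the basis of a further increase in sum of measures", the threshold being 5 mm.

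Section 4.5.4 separately covers the case where the investigator "determines new treatment for breast cancer is warranted, the study treatment may be discontinued".

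**The concern.** The stopping rule and the response criteria describe the same scan finding in different terms, although both carry the iRECIST name. A clinician who follows 4.5.1 stops the drug at the first new lesion or the first qualifying increase. A clinician who follows Table 4 codes that finding as unconfirmed and weighs clinical stability before deciding. The two cannot both be followed for a clinically stable patient whom the clinician would keep on treatment.

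What is at stake is mainly consistent dosing. Patients with the same scan could be handled differently, and a stable patient could lose the study drug on a finding that the protocol does not yet regard as progression. The primary endpoint in Section 7.0 is built on iCR, iPR and iSD, and Table 4 allows each of these after iUPD. It is therefore reasonable to ask whether the mismatch also reaches the endpoint.

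**Working it through.** This is a comparison of text. No figure in Section 7.0 is disputed. An exact binomial calculation reproduces both two-stage designs: 12 then 35 patients gives a type I error of 0.0977 and power of 0.9014; 21 then 50 gives 0.0979 and 0.9008.

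1. **New lesion.** 4.5.1 calls it progression, as does Table 4's RECIST 1.1 column. Table 4's iRECIST column calls it iUPD, with iCPD depending on the next assessment. So the note in 4.5.1 follows the column that the protocol did not adopt.

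2. **Target-lesion increase of 20% and 5 mm.** 4.5.1 calls it progression. Table 5 codes it iUPD at first occurrence, and it stays iUPD unless the sum rises by a further 5 mm or more.

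3. **Confirmation.** 4.5.1 has no such step. Table 4 requires confirmation under iRECIST and, under RECIST 1.1, does not unless the finding is equivocal.

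4. **Clinical stability.** 4.5.1 does not mention it. Table 4 makes it part of the decision on treatment after iUPD. With an automatic stop at the finding, that row has nothing left to govern.

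5. **A limit on the comparison.** The rapid-growth limb of 4.5.1 does not appear in Table 4's RECIST 1.1 column, so 4.5.1 is not simply RECIST 1.1. The mismatch lies in the other two limbs.

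6. **The month-4 endpoint.** Take a clinically stable patient with a first iUPD who is taken off drug. The next scan could give iCPD or, as Table 4 permits, iSD or better, which Section 7.0 counts as disease control. For the early stop to cost the trial a control, one of three things must happen: no further scan is done, a rule counts the patient as a failure, or control is lost because the drug was withdrawn. Section 4.6.2 does not list stopping at iUPD among its non-evaluable categories. The secondary intent-to-treat analysis in Section 7.0 counts early drop-outs as progression but does not say that coming off drug at iUPD is dropping out. The documents give no rate at which iUPD goes unconfirmed. No effect size can be derived.

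7. **Extra time on drug if dosing continues to the next scan.** The flow chart in Section 5.0 appears to mark imaging in alternate cycles through cycle 8 and in each cycle afterwards. Cycles 1–8 last 3 weeks, so the gap is 2 × 3 = 6 weeks, or two 200 mg doses. From cycle 9, cycles last 6 weeks, so the gap is 1 × 6 = 6 weeks, or one 400 mg dose. Imaging follows standard of care and may be earlier if clinically indicated, so six weeks is nominal.

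**The case against.** The strongest reply is that Section 4.5 governs dosing while Tables 4 and 5 classify response. A protocol may assess by iRECIST and still stop drug at first progression, and no row of either table orders treatment beyond iUPD. That much stands: a reader might infer that 4.5.1 breaks a rule requiring continuation, and there is no such rule. What remains is that 4.5.1 labels its stop as iRECIST, and that Table 4's clinical-stability row is itself about treatment.

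A second reply is that the heading imports iRECIST confirmation, with Appendix J supplying the detail. The absence of a confirmation step is indeed partly a matter of silence. But the new-lesion note contradicts Table 4's iRECIST column outright, and Section 4.6.1 cites Appendix J only for more detail on the guideline.

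A third reply is that stopping early protects patients. Section 3.1.2 gives median treatment durations in metastatic TNBC of 11.9, 9 and 4 weeks by line, and Section 3.1.7 expects most metastatic IBC patients to progress within 4 months. Six more weeks on a failing drug is material. That is a real cost, but Section 4.5.4 already lets the investigator stop when new therapy is warranted. Relabelling 4.5.1 as a stop at iUPD would also remove the mislabelling, but it would still leave Table 4's clinical-stability row without a function.

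Two stronger readings are tempting. One is that patients stopped at iUPD are lost as controls and power falls. No text makes such a patient a non-control, and any percentage loss fed into a power calculation would be assumed, so the resulting figure would not show harm. The other is that an iUPD found late in the four months cannot be resolved in time. That treats 4 × 365.25/12 = 121.75 days as a hard cutoff. Section 7.0 refers to 4 months or more and defines no window. If scans fell at the end of even-numbered cycles (an assumption), a week-12 iUPD would be re-scanned at week 18, day 126, only 126 − 121.75 = 4.25 days later.

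**Conclusion.** The point holds as an inconsistency in a treatment-stopping rule. Two limbs of 4.5.1 carry no confirmation step despite the iRECIST heading, so a clinically stable patient stops MK-3475 at a finding that Tables 4 and 5 classify as iUPD, and the clinical-stability consideration is bypassed. The conclusion rests on reading 4.5 and 4.5.1 as written and on nothing in the documents available here reconciling them with the tables.

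Its effect on the month-4 disease control rate cannot be sized from the documents and may be zero. It does not call the two-stage designs or their error rates into question. It should be corrected because the rule conflicts with the criteria the protocol adopted and the correction is cheap.

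**What to change.** Rewrite 4.5.1 in the terms of Tables 4 and 5: discontinue at iCPD, or at iUPD if the patient is clinically unstable or the investigator judges under 4.5.4 that new therapy is warranted. For patients who stop at iUPD, state that the next scheduled or standard-of-care scan, taken before new anticancer therapy where feasible, assigns iCPD or iSD for the primary endpoint.

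This is a wording change to 4.5.1 plus a sentence on classification. Because it uses a scheduled or standard-of-care scan, it should add little imaging. Its downside is the added exposure set out above for stable iUPD patients who turn out to be truly progressing. The stops for clinical instability and for investigator judgement limit that exposure.

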4.6 Criteria for Disease Control

The purpose of this study is to maintain disease control status of patients with metastatic IBC who have achieved clinical response from prior systemic therapy for metastatic disease. PI will be responsible to monitor disease control status. Date of disease progression will be documented and recorded in the study specific database.

4.6.1. Definition of Treatment Response

We will use iRECIST criteria to evaluate and define the treatment response by following the guideline which released in the Lancet Oncology on March 2017⁵⁶.

iRECIST was developed by the RECIST working group for the use of modified Response Evaluation Criteria in Solid Tumours (RECIST version 1.1) in cancer immunotherapy trials, to ensure consistent design and data collection, facilitate the ongoing collection of trial data, and ultimate validation of the guideline. This guideline describes a standard approach to solid tumour measurements and definitions for objective change in tumour size for use in trials in which an immunotherapy is used. Additionally, it defines the minimum datapoints required from future trials and those currently in development to facilitate the compilation of a data warehouse to use

to later validate iRECIST.

Terminology of iRECIST

iRECIST is based on RECIST 1.1. Responses assigned using iRECIST have a prefix of “i” (ie, immune)—eg, “immune” complete response (iCR) or partial response (iPR), and unconfirmed progressive disease (iUPD) or confirmed progressive disease (iCPD) to differentiate them from responses assigned using RECIST 1.1. Similar nomenclature is used for stable disease (iSD). New lesions are assessed and subcategorised into those that qualify as target lesions (new lesion, target) or non-target lesions (new lesion, non-target).

iRECIST Criteria

iRECIST criteria are listed in below tables. Table 4 Shows the comparison of RECIST 1.1 and iRECIST. Table 5 shows the assignment of timepoint response using iRECIST. More details about this guideline is available in Appendix J in PDOL or
[http://www.thelancet.com/journals/lanonc/article/PIIS1470-2045\(17\)30074-8/fulltext](http://www.thelancet.com/journals/lanonc/article/PIIS1470-2045(17)30074-8/fulltext)

Table 4: Comparison of RECIST 1.1 and iRECIST

	RECIST 1.1	iRECIST
Definitions of measurable and non-measurable disease; numbers and site of target disease	Measurable lesions are ≥ 10 mm in diameter (≥ 15 mm for nodal lesions); maximum of five lesions (two per organ); all other disease is considered non-target (must be ≥ 10 mm in short axis for nodal disease)	No change from RECIST 1.1; however, new lesions are assessed as per RECIST 1.1 but are recorded separately on the case report form (but not included in the sum of lesions for target lesions identified at baseline)
Complete response, partial response, or stable disease	Cannot have met criteria for progression before complete response, partial response, or stable disease	Can have had iUPD (one or more instances), but not iCPD, before iCR, iPR, or iSD
Confirmation of complete response or partial response	Only required for non-randomised trials	As per RECIST 1.1
Confirmation of stable disease	Not required	As per RECIST 1.1
New lesions	Result in progression; recorded but not measured	Results in iUPD but iCPD is only assigned on the basis of this category if at next assessment additional new lesions appear or an increase in size of new lesions is seen (≥ 5 mm for sum of new lesion target or any increase in new lesion non-target); the appearance of new lesions when none have previously been recorded, can also confirm iCPD
Independent blinded review and central collection of scans	Recommended in some circumstances—eg, in some trials with progression-based endpoints planned for marketing approval	Collection of scans (but not independent review) recommended for all trials
Confirmation of progression	Not required (unless equivocal)	Required
Consideration of clinical status	Not included in assessment	Clinical stability is considered when deciding whether treatment is continued after iUPD

Table 5: Assignment of timepoint response using iRECIST

	Timepoint response with no previous iUPD in any category	Timepoint response with previous iUPD in any category*
Target lesions: iCR; non-target lesions: iCR; new lesions: no	iCR	iCR
Target lesions: iCR; non-target lesions: non-iCR/non-iUPD; new lesions: no	iPR	iPR
Target lesions: iPR; non-target lesions: non-iCR/non-iUPD; new lesions: no	iPR	iPR
Target lesions: iSD; non-target lesions: non-iCR/non-iUPD; new lesions: no	iSD	iSD
Target lesions: iUPD with no change, or with a decrease from last timepoint; non-target lesions: iUPD with no change, or decrease from last timepoint; new lesions: yes	Not applicable	New lesions confirm iCPD if new lesions were previously identified and they have increased in size (≥ 5 mm in sum of measures for new lesion target or any increase for new lesion non-target) or number; if no change is seen in new lesions (size or number) from last timepoint, assignment remains iUPD
Target lesions: iSD, iPR, iCR; non-target lesions: iUPD; new lesions: no	iUPD	Remains iUPD unless iCPD is confirmed on the basis of a further increase in the size of non-target disease (does not need to meet RECIST 1.1 criteria for unequivocal progression)
Target lesions: iUPD; non-target lesions: non-iCR/non-iUPD, or iCR; new lesions: no	iUPD	Remains iUPD unless iCPD is confirmed on the basis of a further increase in sum of measures ≥ 5 mm; otherwise, assignment remains iUPD
Target lesions: iUPD; non-target lesions: iUPD; new lesions: no	iUPD	Remains iUPD unless iCPD is confirmed based on a further increase in previously identified target lesion iUPD in sum of measures ≥ 5 mm or non-target lesion iUPD (previous assessment need not have shown unequivocal progression)

Target lesions: iUPD; non-target lesions: iUPD; new lesions: yes	iUPD	Remains iUPD unless iCPD is confirmed on the basis of a further increase in previously identified target lesion iUPD sum of measures ≥ 5 mm, previously identified non-target lesion iUPD (does not need to be unequivocal), or an increase in the size or number of new lesions previously identified
Target lesions: non-iUPD or progression; non-target lesions: non-iUPD or progression; new lesions: yes	iUPD	Remains iUPD unless iCPD is confirmed on the basis of an increase in the size or number of new lesions previously identified

* non-iCR/non-iUPD = criteria for neither CR nor PD have been met.

4.6.2. Response will not be considered evaluable in the following categories:

4.6.2.1. Early Deaths: Patients who die within the first 2 weeks of the initiation of drug therapy owing to concurrent disease. These cases will be considered treatment failures in the intent-to-treat analysis.

4.6.2.2. Lost to Follow-up: Patients for whom there is inadequate information to judge tumor response because of loss of contact with our institution (>2 months after a missed appointment) and with referring physician in spite of repeated attempts to locate them. These cases will be considered treatment failures in the intent-to-treat analysis.

4.6.2.3. Major Protocol Violation: Patients who significantly deviate from the treatment program by either adding or deleting another agent or another therapeutic maneuver or by modifying schedule substantially (delay treatment ≥ 7 days without administration reason) of the drug under evaluation. Patients who do not fulfill the requirements outlined under Patient Eligibility are also included in this category. .

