4.3.2 Prohibited Concomitant Medications

Subjects are prohibited from receiving the following therapies during the study.

- Any anti-cancer agents.
- Radiation therapy
 - Note: Radiation therapy to a symptomatic solitary lesion or to the brain will be allowed.
- Live vaccines within 30 days prior to the first dose of trial treatment and while participating in the trial. Examples of live vaccines include, but are not limited to, the following: measles, mumps, rubella, chicken pox, yellow fever, rabies, BCG, and typhoid (oral) vaccine. Seasonal influenza vaccines for injection are generally killed virus vaccines and are allowed; however intranasal influenza vaccines (e.g. Flu-Mist®) are live attenuated vaccines, and are not allowed.
- Glucocorticoids for any purpose other than to modulate symptoms of suspected immunologic etiology.

Subjects who, in the assessment by the investigator, require the use of any of the aforementioned treatments for clinical management should be removed from the trial. Subjects may receive other medications that the investigator deems to be medically necessary.

There are no prohibited therapies during the Post-Treatment Follow-up Phase.

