7.0 STATISTICAL ANALYSIS PLAN

The primary objective of this phase II trial is to assess the efficacy of MK-3475 as a single agent in metastatic IBC and non-IBC TNBC patients. The primary endpoint is the rate of disease control measured at the end of 4 months from the start of therapy.

The disease control rate is defined as the percentage of patients either 1) with measurable disease that achieve iCR, iPR, iSD, or 2) with non-measurable disease that achieve iCR or iSD, , by 4 months or more in all evaluable patients. We will also perform secondary analysis on intent-to-treat patient population where those patients who drop out early will be considered as progression.

The trial will be conducted using Simon's optimal two-stage design and the rate of disease control will be estimated accordingly. It is assumed that the MK-3475 single agent will have a disease control rate of 30%. A disease control rate of 10% or lower will be considered treatment failure and the regimen will be rejected under this circumstance. When the probability of accepting a "bad" regimen (i.e. disease control rate 10% or lower) is 0.10 and the probability of rejecting a "good" regimen (i.e. disease control rate 30% or higher) is also 0.10, Simon's optimal 2-stage design requires 12 patients enter in the first stage. The study accrual will be delayed until all 12 patients are evaluable for disease control status. If 1 or no patients maintain disease control on treatment, the trial will be stopped and the regimen will be declared as ineffective. If 2 or more patients maintain disease control, 23 more patients will be enrolled to the study to reach a total of 35 treated patients. By the end of the study, the new regimen will be rejected if rate of disease control is less than or equal to 5/35 and will be considered worthy of further investigation otherwise.

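### A patient who starts another anti-cancer agent before month 4 can become non-evaluable and leave the primary denominator instead of counting as a failure

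*Combined protocol and SAP*

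**What the plan says.** Section 4.6.2 opens with "Response will not be considered evaluable in the following categories" and lists three: early deaths, losses to follow-up and major protocol violations. The third, Section 4.6.2.3, covers "Patients who significantly deviate from the treatment program by either adding or deleting another agent or another therapeutic maneuver", together with substantial schedule changes and ineligible patients. For the first two categories the protocol adds "These cases will be considered treatment failures in the intent-to-treat analysis". Section 4.6.2.3 has no such sentence.

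Section 7.0 sets the endpoint: "The primary endpoint is the rate of disease control measured at the end of 4 months from the start of therapy". Control means iCR, iPR or iSD (iCR or iSD for non-measurable disease), and the rate is taken "by 4 months or more in all evaluable patients". A secondary intent-to-treat analysis follows, in which "those patients who drop out early will be considered as progression".

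Two other sections deal with new anti-cancer treatment, and neither says how the patient counts for the endpoint. Under Section 4.5.4, where the investigator "determines new treatment for breast cancer is warranted, the study treatment may be discontinued". Under Section 4.3.2, patients who "require the use of any of the aforementioned treatments for clinical management should be removed from the trial".

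Section 7.0 states its sample sizes, 35 and 50, as treated patients. It words its final cut-offs, 5/35 and 7/50, as rates. It gives no rule for replacing non-evaluable patients.

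**The concern.** The hypothesis in Section 2.1 is that MK-3475 maintains disease control. A patient who needs other systemic therapy within four months has usually lost it. If that patient is set aside as non-evaluable, the primary analysis loses a failure, and in most cases the error favours the drug.

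The trial is single-arm and open-label, and Section 4.6 makes the principal investigator responsible for monitoring disease control status. Whether a patient is a failure or a protocol violator may thus be settled by someone who already knows the outcome. At stake are the reported rate, its 95% exact interval and, on one reading of the cut-off, the error rate of the final decision.

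**Working it through.** **Inputs.** From Section 7.0: null rate 10%; error limits 0.10 and 0.10; design A (target 30%) stops at 1 or fewer of 12 and rejects at 5/35 or below; design B (target 25%) stops at 2 or fewer of 21 and rejects at 7/50 or below. The Trial Summary gives 50 subjects. The documents give no frequency of starting another agent, so the number excluded, k, and the share excluded, d, are assumptions.

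**Step 1: the plan's own designs.** For design B the probability of acceptance is P(X21 ≥ 3 and X50 ≥ 8), from exact binomials summed over stage 1 results.
- Design B: 0.0979 at 10%, 0.9008 at 25%.
- Design A: 0.0977 at 10%, 0.9014 at 30%.

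Both designs reproduce and meet their stated limits.

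**Step 2: reported rate.** With x controlled among n treated, and k non-controlled patients excluded, the rate moves from x/n to x/(n − k). It rises whenever x > 0. Example: 8/50 = 16.0%, exact 95% interval 7.2% to 29.1%. With five excluded, 8/45 = 17.8%, interval 8.0% to 32.1%. (Clopper-Pearson limits: the 0.025 quantile of Beta(x, m − x + 1) and the 0.975 quantile of Beta(x + 1, m − x), where m is the denominator.)

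**Step 3: decision, three readings of the cut-off at a true all-treated rate of 10%.**

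(a) *Count over all treated patients.* Eight controlled patients are still needed. Type I error stays at 0.098.

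(b) *Rate above 7/50, no replacement, all k exclusions non-controlled and in stage 2.* The requirement is the smallest x with x/(50 − k) > 0.14, and the error is P(X21 ≥ 3 and X50 ≥ x).

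| k | Smallest passing result | Type I error |
|---|---|---|
| 0 | 8/50 = 16.0% | 0.098 |
| 1 | 7/49 = 14.3% | 0.166 |
| 5 | 7/45 = 15.6% | 0.166 |
| 10 | 6/40 = 15.0% | 0.243 |

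One exclusion is enough for the first step. In design A, one exclusion lets 5/34 = 14.7% pass where 5/35 = 14.3% is rejected, and the error goes from 0.098 to 0.176.

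(c) *Excluded patients, all non-controlled, are replaced until the evaluable number is 50 or 35.* A true rate of 10% then appears as 0.10/(1 − d).

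| d | Apparent rate | Type I error, design B | Type I error, design A |
|---|---|---|---|
| 5% | 10.5% | 0.121 | 0.117 |
| 10% | 11.1% | 0.151 | 0.141 |
| 15% | 11.8% | 0.188 | 0.169 |
| 20% | 12.5% | 0.233 | 0.204 |

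**Step 4: with the change.** If these patients count as failures and the denominator is all treated patients, n stays at 35 or 50 and the error at 0.098.

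**The case against.** A reader might infer that everyone switched to new therapy before month 4 drops out of the primary analysis, and that a patient switched after a first, unconfirmed progression cannot be counted as a failure because confirmed progression was never reached. The documents do not support that much.

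- Control is credited only for iCR, iPR or iSD, so a patient whose last status is iUPD is not in the numerator. Section 4.5.1 defines progression for stopping treatment without a confirmation step, and Section 4.6 has the progression date recorded. No text says that later therapy erases it. But no text says that it takes precedence over Section 4.6.2.3 either.
- Section 4.5.4 is a listed reason to end MK-3475, and Section 4.3.2 prohibits no therapy during post-treatment follow-up. A patient who stops first and switches afterwards can be read as having followed the protocol. Section 4.6.2.3 fits more naturally an agent added while MK-3475 continues.
- Removal under Section 4.3.2 plausibly makes the patient an early dropout, and hence a progression in the intent-to-treat analysis. That analysis is secondary, and it does not name these patients.
- A reader might also see a direct conflict between Sections 4.5.4 and 4.3.2. They are only loosely at odds, since neither authorises MK-3475 beside a new anti-cancer agent.
- The direction is not fixed. If an excluded patient would have been counted as controlled, the rate falls: 8/50 = 16.0% becomes 7/49 = 14.3%.
- Analysing evaluable patients first and all patients second is a declared choice, not an oversight.

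These points narrow the exposure to patients who start another agent before month 4 without recorded progression, or while still on MK-3475. They do not remove it, because the text supplies neither the failure sentence nor an order of precedence.

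**Conclusion.** The concern holds in this limited form. As written, Sections 4.6.2.3 and 7.0 together allow a patient who starts another systemic anti-cancer agent before month 4 to be dropped from the primary rate, and the intent-to-treat analysis does not clearly recover that patient. Relative to counting such patients as failures, the reported rate and its interval rise.

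The inflated error rates in readings (b) and (c) should not be taken as the trial's actual type I error. They rest on the cut-off being applied to evaluable patients, on assumed numbers of exclusions, and on every excluded patient being non-controlled; reading (b) also places all exclusions in stage 2. If the cut-off is a count over treated patients, the decision is unaffected. The documents do not settle which denominator governs, and that is itself part of the defect. The text should be changed; the size of the bias cannot be determined from it.

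**What to change.** 1. In Section 4.6.2.3, remove the addition of another systemic anti-cancer agent as a ground for non-evaluability.
2. In Section 7.0, state that starting such therapy before the 4-month assessment counts as no disease control in both the primary and the intent-to-treat analysis.
3. In the same place, state that progression recorded earlier stands as a failure whatever follows, and that the 7/50 (or 5/35) rule applies to all treated patients.
4. Reconcile the wording of Sections 4.5.4 and 4.3.2. Which treatment rule applies is for the sponsor to decide.

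The cost is a few sentences, with no extra visits, data or patients. The observed disease control rate may come out slightly lower.
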